A Validation of the Assisted Fluid Management Feature

CLINICAL STUDY PROTOCOL

Medical Device: EV1000 Platform with Acumen[™] Assisted Fluid Management Feature

Date: October 25, 2018

NCT03469570

Title:	A Validation of the Acumen [™] Assisted Fluid Management (AFM)
Short Title:	AFM Study
Purpose:	The primary objective of this study is to evaluate the performance of the Acumen TM Assisted Fluid Management (AFM) Feature in its ability to predict a subject's fluid responsiveness. The validity of the fluid bolus recommendation will be analyzed by reporting the number of recommendations followed by delivered boluses that did and did not have a stroke volume response meeting the set fluid strategy.
	Subjects enrolled in the validation study will have their fluid management decisions guided by the AFM Feature. The decision to provide fluid as recommended by the AFM Feature lies solely with the treating investigator. When a fluid recommendation is made by the AFM Feature, the investigator will assess the subject holistically prior to accepting or declining the system recommendation.
Device Name:	Edwards Lifesciences Acumen [™] Assisted Fluid Management (AFM) software
Overall Design:	Pragmatic, multi-site, clinical study with subjects allocated to a single arm
Sample Size:	330 Subjects
Number of Sites:	Up to 20 sites
Subject Participation:	 Subject participation will include: Screening / consent Placement of arterial line and use of Edwards FloTrac IQ Undergo planned surgical procedure Fluid management during surgical procedure Data Collection Device related adverse event/serious adverse event data collection, if applicable
	Anti-instant to lost (months

Enrollment Period: Anticipated to last 6 months

	Inclusion Criteria:
	1. Be \geq 18 years of age
	2. Non-cardiac/Non-thoracic surgery (e.g., abdominal surgery, combined abdominal/pelvic surgery, major peripheral vascular surgery) expected to last >2 hours post anesthesia induction
	3. Procedure will require Mechanical ventilation
	4. American Society of Anesthesiology (ASA) Score 3 or 4
	5. Expected arterial line placement for surgical procedure and general anesthesia
	6. Projected to receive hemodynamic monitoring during surgical procedure
	 Participate or have authorized representative participate in the Informed Consent process and sign/date the IRB approved informed consent form
	Exclusion Criteria
	8. Are < 18 years of age
	9. Have a body mass index \geq 35 kg/m ²
Clinical Study Population:	10. Known acute congestive heart failure
	11. Known aortic stenosis with valve area $\leq 1.5 \text{ cm}^2$
	12. Known moderate to severe aortic regurgitation
	13. Known moderate to severe mitral regurgitation
	14. Known moderate to severe mitral stenosis
	15. Current persistent atrial fibrillation
	16. Liver resection procedure
	17. Neurosurgery
	18. Open chest procedures
	19. Patient or surgical procedure type known as an SVV limitation ¹⁶ (e.g. tidal volume <8mL/kg of theoretical ideal weight, spontaneous ventilation, persistent cardiac arrhythmia, known atrial fibrillation, open chest surgery, Heart Rate/Respiratory Rate (HR/RR) ratio <3.6)
	20. Emergent or cardiovascular surgical procedure
	21. Patient who is confirmed to be pregnant
	22. Participation in any other drug, device, or biologic study concomitantly, or within the last 30 days (which may clinically interfere with this Clinical Study)
	23. Refusal of patient or authorized representative to sign consent
	Primary effectiveness endpoint:
Endpoints:	Evaluate the performance of the AFM feature in its ability to predict the fluid responsiveness of a subject.

Primary safety endpoint:

The primary safety endpoint is the assessment of serious adverse events which may be related to the AcumenTM Assisted Fluid Management Feature.

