## Statistical Analysis Plan (SAP)

Data will be summarized using standard frequentist methods as appropriate per data type, i.e. frequencies (percentages) for categorical data, means, medians, measures of dispersion for continuous data and will be reported overall and by group. Any AE's will also be listed and summarized by site and group. All of the primary analysis will be on the intent to treat (ITT) population. Histograms and boxplots will be used to check distributions and for possible outliers for continuous variables. Mathematical transformations will be applied where appropriate in order to render the continuous variables to a normal distribution. Even if consistency with a normal distribution is found, all descriptive statistics will be reported with 97.5% confidence intervals, estimated from both bootstrapped and traditional estimation methods. Similarly, if not a normal distribution (i.e. proportion, etc.) then the point estimate and one-sided 97.5% confidence interval for the primary effectiveness endpoint recommended at the event level will also be computed using a bootstrap methodology and traditional estimation methods. Following the suggestions of Samuelson and Petrick (2006) a minimum threshold of 4000 bootstrap iterations is recommended for an alpha=0.025.

This approach is recommended for non-Gaussian distributions since it can accommodate correlated data. Any bootstrapping will follow procedure as discussed by Davison, AC and Hinkley, DV (1997). All statistical analysis will be conducted using SAS v9.4 or higher (Cary, NC) or NCSS v11 or higher (Kaysville, Utah, 2016) where specified.

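### Does exclusion 20, on cardiovascular procedures, shut out the peripheral vascular surgery that inclusion 2 names as eligible?

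*Protocol*

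**What the plan says.** Two lines of the protocol's Clinical Study Population section matter here.

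- Inclusion 2 describes the eligible surgery: "Non-cardiac/Non-thoracic surgery (e.g., abdominal surgery, combined abdominal/pelvic surgery, major peripheral vascular surgery", among other examples of the same kind, expected to last more than two hours after induction.
- Exclusion 20 bars an "Emergent or cardiovascular surgical procedure".

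Two neighbouring exclusions also concern the type of procedure: exclusion 18, "Open chest procedures", and exclusion 19, "Patient or surgical procedure type known as an SVV limitation". Neither mentions peripheral vascular surgery, and neither defines 'cardiovascular'. That word occurs once in the text available, in exclusion 20.

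For the analysis, the Purpose section says validity will be judged by "reporting the number of recommendations followed by delivered boluses that did and did not have a stroke volume response meeting the set fluid strategy". The SAP states that "All of the primary analysis will be on the intent to treat (ITT) population", and it plans a "one-sided 97.5% confidence interval for the primary effectiveness endpoint recommended at the event level will also be computed using a bootstrap methodology" as well as traditional estimation. The SAP text available says nothing about eligibility.

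**The concern.** In ordinary use, 'cardiovascular' means heart and blood vessels. On that meaning, a patient listed for a major peripheral vascular operation meets inclusion 2 by name and is then caught by exclusion 20. Eligibility requires every inclusion and no exclusion, so the exclusion would win.

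Up to 20 sites apply these lines independently. Two sites could classify the same patient differently in good faith. One might enrol vascular cases that another would log as eligibility deviations. A reader might then be unsure whether the reported performance of the AFM Feature extends to that kind of surgery. In a single-arm validation study, the enrolled case mix defines the population to which the result applies, so the question is a fair one.

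**Working it through.** The plan has no figure of its own to reproduce on this point. The check is mainly one of wording.

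**Step 1: how the exclusion list is built.** Much of it duplicates other criteria.

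| Exclusion | Relation to other criteria |
|---|---|
| 8 (under 18) | Negative of inclusion 1 |
| 23 (refusal of consent) | Negative of the consent inclusion |
| 18 (open chest) | Counterpart of 'non-thoracic' in inclusion 2; repeated within 19 |
| 15 (persistent atrial fibrillation) | Overlaps 19 |

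In a list of this kind, redundancy is not evidence that an item must add something new. Exclusion 20 fits as the counterpart of 'non-cardiac', much as exclusion 18 is of 'non-thoracic'.

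**Step 2: try both readings.**

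- Narrow reading (cardiac or central-vessel surgery): inclusion 2 and exclusion 20 are both satisfiable, and every example in inclusion 2 keeps its function.
- Broad reading (any vessel): the peripheral vascular example in inclusion 2 could never lead to enrolment.

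Where the list does take an operation out of an otherwise eligible class, it names the operation. Exclusion 16 removes liver resection from abdominal surgery in this way. Exclusion 20 names no peripheral vascular procedure.

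**Step 3: what a difference in reading could do to the estimate.** Let s be the share of analysed boluses from peripheral vascular cases, p_v their response proportion, p_o the proportion in all other cases, and d = p_v − p_o. The primary proportion with vascular cases, minus that without, is

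[(1 − s)p_o + s·p_v] − p_o = s × d.

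The documents give neither s nor d. Assumed range: s from 5% to 30%, d from 5 to 20 points.

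- s = 5%, d = 5: 0.25 points
- s = 10%, d = 10: 1.0 point
- s = 20%, d = 20: 4.0 points
- s = 30%, d = 20: 6.0 points

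For scale, take the planned 330 subjects, with one bolus each and a proportion of 50% (both assumed). A one-sided 97.5% bound then lies 1.96 × √(0.25/330) = 5.4 points from the estimate. The shift reaches that distance at s = 5.4/20 = 27% when d = 20, or at d = 5.4/0.30 = 18 points when s = 30%.

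The yardstick is itself fragile. With three independent boluses per subject (also assumed), it becomes 1.96 × √(0.25/990) = 3.1 points, and correlation within subjects would change it again. The same grid could be attached to any eligibility ambiguity. It bounds a hypothetical and is not evidence of an effect.

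**The case for a change.** The best case for a change is that the protocol writes 'non-cardiac' in one place and a broader word in another, and a screener cannot know whether the difference was deliberate. If exclusion 20 meant only heart surgery, it would largely repeat inclusion 2 and overlap exclusion 18, so a careful reader might infer that it was meant to add vessel surgery. An example in an inclusion does not override an exclusion. A clarification would cost one line and a site notice.

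Part of this stands. The term is undefined in the text available, the narrow reading is nowhere written down, and a sponsor who tidied the wording would do no harm. The inference from redundancy is weak, however, because this list repeats itself freely. The cheapness of a fix is also not a gain in itself. Nothing in the documents shows that sites read the lines differently.

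A further suggestion would be a descriptive row giving the primary proportion with and without vascular cases. It would tell little. If vascular cases were 10% of the sample (33 of 330, assumed, one bolus each, proportion 50%), their own estimate would carry 1.96 × √(0.25/33) = 17.1 points of uncertainty on one side.

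**Conclusion.** This is a gap in wording that sites and analysts can fill sensibly, and it needs no change to the plan. The two criteria are compatible on the reading that the list's structure favours, and the opposite reading cancels an operation the protocol expressly names.

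The primary analysis is unaffected in kind. With a single arm there is no comparison to distort, and the proportion remains a valid summary for the subjects enrolled. What could vary is the case mix, which a tabulation of procedures would show. The SAP plans frequencies for categorical data, though it does not list procedure type.

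No size or direction of effect is shown. The 0.25 to 6.0 point range rests entirely on assumed shares and differences.

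The conclusion assumes that sites read exclusion 20 in line with the example in inclusion 2. Evidence that sites had turned away vascular cases, or had logged them as deviations, would reopen the question. Part of the SAP is not in the text available, so a definition given there cannot be ruled out.

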## Statistical Analysis Plan (SAP)

Data will be summarized using standard frequentist methods as appropriate per data type, i.e. frequencies (percentages) for categorical data, means, medians, measures of dispersion for continuous data and will be reported overall and by group. Any AE's will also be listed and summarized by site and group. All of the primary analysis will be on the intent to treat (ITT) population. Histograms and boxplots will be used to check distributions and for possible outliers for continuous variables. Mathematical transformations will be applied where appropriate in order to render the continuous variables to a normal distribution. Even if consistency with a normal distribution is found, all descriptive statistics will be reported with 97.5% confidence intervals, estimated from both bootstrapped and traditional estimation methods. Similarly, if not a normal distribution (i.e. proportion, etc.) then the point estimate and one-sided 97.5% confidence interval for the primary effectiveness endpoint recommended at the event level will also be computed using a bootstrap methodology and traditional estimation methods. Following the suggestions of Samuelson and Petrick (2006) a minimum threshold of 4000 bootstrap iterations is recommended for an alpha=0.025.

This approach is recommended for non-Gaussian distributions since it can accommodate correlated data. Any bootstrapping will follow procedure as discussed by Davison, AC and Hinkley, DV (1997). All statistical analysis will be conducted using SAS v9.4 or higher (Cary, NC) or NCSS v11 or higher (Kaysville, Utah, 2016) where specified.

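### Does naming an ITT population clash with a primary estimate built on delivered-bolus events?

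*SAP*

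**What the plan says.** The SAP, in the section headed Statistical Analysis Plan (SAP), says: "All of the primary analysis will be on the intent to treat (ITT) population". It later specifies a "one-sided 97.5% confidence interval for the primary effectiveness endpoint recommended at the event level". That clause is conditional on the data not being normal, but it names proportions as an instance, so it applies to a response rate.

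The protocol synopsis, under Purpose, describes the analysis as reporting the "number of recommendations followed by delivered boluses that did and did not have a stroke volume response meeting the set fluid strategy". The same entry says "The decision to provide fluid as recommended by the AFM Feature lies solely with the treating investigator", and that "the investigator will assess the subject holistically prior to accepting or declining the system recommendation". Under Overall Design the study is a "Pragmatic, multi-site, clinical study with subjects allocated to a single arm". Under Endpoints, the primary effectiveness endpoint reads only: "Evaluate the performance of the AFM feature in its ability to predict the fluid responsiveness of a subject". A primary safety endpoint, on serious adverse events possibly related to the feature, is listed beside it.

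The text available is the protocol synopsis and this one SAP section. It contains no definition of ITT, but an earlier part of the SAP and the protocol body were not available and may hold one.

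**The concern.** ITT normally means analysing everyone as randomised. With one arm there is no randomisation to give the term that meaning, so it needs a definition. ITT is also a statement about subjects, whereas the primary interval concerns events, and the synopsis admits only events in which the investigator chose to give fluid. An enrolled subject who never received a recommended bolus could belong to the ITT population and yet contribute nothing to the rate.

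What is at stake is the reach of the conclusion. This is a validation of a recommendation feature. A result headed ITT might be taken to cover every enrolled subject or every recommendation issued, when it is a response rate among recommendations the investigator accepted and acted on. If investigators tend to decline the less plausible recommendations, those two quantities differ.

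**Working it through.** **Figures that can be reproduced.** The one-sided 97.5% limit implies alpha = 1 - 0.975 = 0.025, which matches the SAP's stated alpha. The sample size of 330 subjects cannot be reproduced, because the text available gives no expected rate, performance goal, power or number of events per subject. The question is one of definition, so the check is whether the population label can alter the result.

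**Step 1: does including subjects without events change the rate?** Let subject i have B_i delivered recommended boluses, of which R_i met the response criterion. The event-level rate is

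p = ΣR_i / ΣB_i.

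A subject with B_i = 0 has R_i = 0 and adds nothing to either sum. The rate over all 330 subjects therefore equals the rate over those with at least one delivered bolus.

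**Step 2: does it change the interval?** An interval based on the events alone is unaffected, since such subjects hold no events. If the bootstrap resamples subjects, the first-order variance of p is

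Σ(R_i - pB_i)² / (ΣB_i)²,

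and a subject with B_i = R_i = 0 again contributes zero. The SAP does not state the resampling unit, but the conclusion is the same either way.

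**Step 3: how many subjects might this concern?** The documents give no bolus counts, so these are assumptions. With a mean of m boluses per subject:

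| m | Poisson, 330·exp(-m) | Negative binomial (k = 1), 330/(1 + m) |
|---|---|---|
| 1 | 121.4 | 165.0 |
| 2 | 44.7 | 110.0 |
| 3 | 16.4 | 82.5 |

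The number could be substantial, but by steps 1 and 2 none of these subjects moves the rate or its first-order variance.

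**Step 4: what would a literal reading over all recommendations do?** Let p be the response rate among delivered boluses and D the share of recommendations delivered. Scoring undelivered recommendations as non-response gives pD, lower by p(1 - D):

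| D | p = 0.5 | p = 0.6 | p = 0.7 |
|---|---|---|---|
| 0.95 | 0.025 | 0.030 | 0.035 |
| 0.90 | 0.050 | 0.060 | 0.070 |
| 0.70 | 0.150 | 0.180 | 0.210 |

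Scoring them as response gives pD + (1 - D). At p = 0.60 and D = 0.70 the rate is 0.60 × 0.70 = 0.42 under the first rule and 0.42 + 0.30 = 0.72 under the second. The direction depends wholly on an imputation rule that appears nowhere in the documents, for responses that cannot be observed because no bolus was given. These figures size a reading the plan does not invite; they are not a bias in the planned estimate.

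**Step 5: set the texts side by side.** The SAP sentence fixes the subjects. The SAP interval clause fixes the unit. The synopsis Purpose entry fixes which events count and says openly that recommendations may be declined. Read in that order, they give one analysis: take the included subjects, collect their recommendations followed by a delivered bolus, and report the proportion with the required response. No sentence contradicts another.

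**The case for a change.** The best argument for a change is that the term is borrowed from randomised trials, is undefined in the text available, and sits in a validation study where the difference between all recommendations and accepted recommendations matters to users. The SAP also speaks of reporting by group in a single-arm study, which hints at template wording. A few added sentences and a table of recommendations issued, declined and delivered would cost little.

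Part of this stands. The label is loose, and a careful report would say that the rate is conditional on acceptance and delivery and would give the number of subjects with no qualifying event. But the synopsis already tells the reader that the count covers "by reporting the number of recommendations followed by delivered boluses that did and did not have a stroke volume response", and that the investigator decides on delivery. The misreading requires setting that aside. The absence of a definition can be asserted only for the text available. Replacing the ITT sentence with a definition of the effectiveness event set would also do harm: the sentence covers the whole primary analysis, so removing it would leave the primary safety endpoint without a stated population. A table of declined recommendations presupposes records that the available text does not confirm are kept.

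**Conclusion.** The concern does not call for a change. The SAP names a subject population and an event-level unit, which are compatible, and the protocol synopsis supplies the event set. Following the plan as written gives a legitimate rate among delivered recommendations. Under that reading the estimate changes by exactly zero and the interval is unaffected to first order, however many subjects have no delivered bolus. The 2.5 to 21 point gaps arise only if undelivered recommendations are kept and scored as failures, under assumed response and delivery rates, and no text supports that rule.

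What remains is a gap in labelling that analysts would fill sensibly when naming the analysis set and describing the result. The conclusion rests on taking the synopsis Purpose entry as the description of the primary event set, and on nothing in the unavailable parts of the SAP or protocol contradicting it.

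### Do unsided 97.5% intervals for descriptive statistics conflict with the one-sided 97.5% interval for the primary endpoint?

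*SAP*

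**What the plan says.** Everything relevant is in the first paragraph of the section headed Statistical Analysis Plan (SAP), apart from the description of the endpoint, which is in the Purpose entry of the protocol synopsis.

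- **Descriptive statistics.** The SAP states that "all descriptive statistics will be reported with 97.5% confidence intervals, estimated from both bootstrapped and traditional estimation methods". The level is given, the side is not, and the intervals are reported whatever the distribution check shows.
- **Primary effectiveness endpoint.** "if not a normal distribution (i.e. proportion, etc.) then the point estimate and one-sided 97.5% confidence interval for the primary effectiveness endpoint" is to be computed by bootstrap and by traditional methods. The level and one-sidedness are given; whether the bound is lower or upper is not.
- **Distribution check.** "Histograms and boxplots will be used to check distributions and for possible outliers for continuous variables". It is graphical and limited to continuous variables.
- **Alpha.** It appears once, with the size of the bootstrap: "a minimum threshold of 4000 bootstrap iterations is recommended for an alpha=0.025".
- **Endpoint.** The protocol assesses the bolus recommendation by "reporting the number of recommendations followed by delivered boluses that did and did not have a stroke volume response", which is a count out of a total.

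**The concern.** Three things look wrong on a first reading.

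1. A confidence interval with no stated side is usually taken as two-sided. A two-sided 97.5% interval leaves 1.25% in each tail, while a one-sided 97.5% interval leaves 2.5% in one. The two-sided interval whose limit matches the one-sided 97.5% bound is the 95% interval. A reader comparing two limits, both labelled 97.5%, could be comparing limits at different tail areas.
2. The primary interval follows an if-clause about normality. If the form of the primary interval truly depended on how the data looked, its error rate would be uncertain, and the analyst would have a choice to make after seeing the data.
3. The minimum of 4000 bootstrap iterations is tied to alpha = 0.025, but a two-sided 97.5% percentile interval reads the 1.25% tail, where half as many replicates lie.

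If these held, the stake would be the error rate of the primary conclusion and the comparability of the reported limits.

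**Working it through.** **Inputs.** From the SAP: 97.5% with no side (descriptive), 97.5% one-sided (primary), alpha 0.025, 4000 iterations. From the protocol: 330 subjects. Assumed, because the documents do not give it: 330 independent events, one per subject, with a Wald limit. This assumption serves only to put a size on the difference.

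**Step 1. Reproduce the stated alpha.** One-sided non-coverage = 1 − 0.975 = 0.025. The primary interval and the SAP's alpha agree exactly.

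**Step 2. The two readings of the descriptive interval.**

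| Reading | Critical value | Per tail | Total non-coverage |
|---|---|---|---|
| One-sided 97.5% | z(0.975) = 1.960 | 0.025 | 0.025 |
| Two-sided 97.5% | z(0.9875) = 2.241 | 0.0125 | 0.025 |
| Two-sided 95%, for comparison | z(0.975) = 1.960 | 0.025 | 0.05 |

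The label 97.5% means total non-coverage of 0.025 on either reading. Only the split between tails differs, and with it the distance of the limit from the estimate: 2.2414 / 1.9600 = 1.144, about 14%.

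**Step 3. Size on the proportion scale.** Lower limit = p − z × √(p(1 − p)/n). At p = 0.50 and n = 330, the standard error is √(0.25/330) = 0.0275.

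- One-sided 97.5%: 0.50 − 1.960 × 0.0275 = 0.446
- Two-sided 97.5%: 0.50 − 2.241 × 0.0275 = 0.438

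The gap is 0.008. It is 0.007 at p = 0.30 and 0.006 at p = 0.80. Several boluses in one subject would change the standard error, but under a normal approximation the ratio of 1.144 stays the same.

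**Step 4. Does the interval type depend on the data?** For the descriptive intervals it does not, since the SAP reports them even where normality is found. For the primary endpoint, the clause gives a proportion as its example of a non-normal quantity. The protocol's endpoint is a count of recommendations with and without a response, so it is a proportion by definition. The histograms and boxplots apply to continuous variables and do not bear on it. The condition is therefore met before any data exist.

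**Step 5. Bootstrap tail counts.** Replicates beyond the limit: 4000 × 0.025 = 100 for a 2.5% tail, and 4000 × 0.0125 = 50 for a 1.25% tail. The simulation error of the tail area is √(0.025 × 0.975/4000) = 0.0025 and √(0.0125 × 0.9875/4000) = 0.0018 respectively. Dividing by the normal density at each limit (0.0584 and 0.0324) gives about 0.042 and 0.054 standard errors. With the standard error of 0.0275 from Step 3, the simulation error of the limit is about 0.0012 and 0.0015. Both are small beside the sampling error, so 4000 iterations serve either reading.

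**The case for a change.** The best argument for a change is that the primary proportion can fall under both sentences. The SAP lists percentages among its descriptive summaries, so the same estimate could appear once with an unsided 97.5% interval and once with a one-sided 97.5% interval, giving two lower limits under one label. Naming a side in one sentence and omitting it in the one before does suggest that the first is two-sided. The primary bound also has no stated direction, and an if-clause is a poor place for a primary analysis. Two sentences would settle all of this at no cost to the data or the sample size.

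The drafting criticism stands: the side is missing, the direction is missing and the condition is clumsy. The inference drawn from it does not.

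- The two-sided reading is supplied by the reader. The SAP links the primary sentence to the descriptive one as a parallel case, so a shared one-sided convention is also possible. On that reading there is no discrepancy.
- Even with two limits printed, the one for the primary endpoint is identified, because the SAP assigns the one-sided interval to it by name. A reader need not recover it from a descriptive table.
- The purpose is to show how well the feature predicts fluid responsiveness, so a lower bound is the natural direction.
- Reporting descriptive statistics at 95% rather than 97.5% is a matter of convention. A correctly labelled 97.5% interval is not an error.

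**Conclusion.** No change to the plan follows. As written, it yields a one-sided 97.5% interval for the primary proportion, with a tail of 0.025 that matches the stated alpha, and this does not depend on a look at the data. The descriptive intervals test nothing, so they neither use nor alter the type I error of the primary analysis. What remains is an unstated side, worth about 14% in the distance of a limit from its estimate, or 0.006 to 0.008 for proportions of 0.30 to 0.80, and a loosely worded condition. An analyst would resolve both by labelling the tables and reporting the primary lower bound.

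This rests on the primary endpoint being a proportion, as the protocol's Purpose entry describes it, and on the SAP text available here; a side stated elsewhere in the SAP would close the gap altogether. The sizes in proportion units also assume 330 independent events, which the documents do not give. The agreement between the primary interval and alpha needs no such assumption.

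### Read literally, the SAP's interval rule puts a bootstrap interval on the rate of AFM-related SAEs, where it collapses to 0%–0% at zero events; an exact limit should be named instead

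*SAP*

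**What the plan says.** The Protocol synopsis (Endpoints) states: "The primary safety endpoint is the assessment of serious adverse events which may be related to the AcumenTM Assisted Fluid Management Feature". It gives no rate, threshold or hypothesis there. The planned size is 330 subjects (Sample Size), and the design is "Pragmatic, multi-site, clinical study with subjects allocated to a single arm" (Overall Design), so there is no concurrent control rate.

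The SAP, first paragraph, says four things that bear on this endpoint:

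- Categorical data are summarised as counts with percentages.
- For adverse events: "Any AE's will also be listed and summarized by site and group". No interval method is attached to that sentence.
- After sentences on checking and transforming continuous variables, a sentence opens "Even if consistency with a normal distribution is found" and goes on to require that "all descriptive statistics will be reported with 97.5% confidence intervals, estimated from both bootstrapped and traditional estimation methods". It does not say which traditional method, or whether the interval is one- or two-sided.
- The next sentence turns to non-normal quantities such as proportions. Its interval clause reads: "one-sided 97.5% confidence interval for the primary effectiveness endpoint recommended at the event level will also be computed using a bootstrap methodology and traditional estimation". It names only the effectiveness endpoint.

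On the number of resamples, the SAP adds that "a minimum threshold of 4000 bootstrap iterations is recommended for an alpha=0.025".

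**The concern.** An SAE percentage is a descriptive statistic, so the literal wording attaches a bootstrap interval to it. The nonparametric bootstrap learns about variability only from the observed values. If no subject has an event, every resample is a set of zeros and the interval has no width. That reflects the method, and says nothing about the device. A few events help only partly, because the resampling distribution is still built around an estimate that is itself very uncertain.

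Zero or one related SAE is a plausible result here. In a single-arm study, the upper confidence limit is the figure that tells a reader how high a related-SAE rate remains compatible with the data. An interval of 0%–0% withholds that. If it is printed beside a second interval with a very different upper limit, the reader has no stated basis for choosing between them.

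**Working it through.** **Inputs.** n = 330 (Protocol, Sample Size). Confidence level 97.5%, at least 4000 resamples, alpha = 0.025 (SAP). The stated alpha agrees with a one-sided 97.5% interval: 1 − 0.975 = 0.025. The sample size cannot be reproduced, because the available text gives no target rate or power. The documents give no expected SAE rate, so the true rates in step 4 are assumptions.

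**Step 1: zero events, bootstrap and Wald.** Each resample draws 330 values from 330 zeros, so each resampled proportion is 0/330 = 0. All percentiles are 0 and the interval is 0%–0%. A run of 4000 resamples confirmed this. The Wald interval is p̂ ± z·√(p̂(1 − p̂)/n). With p̂ = 0 the standard error is 0, so it is also 0%–0%.

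**Step 2: zero events, methods that do not collapse.**

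- Exact (Clopper-Pearson) upper limit: 1 − a^(1/330).
  - One-sided 97.5%, a = 0.025: 1 − 0.025^(1/330) = 1.11%.
  - Two-sided 97.5%, a = 0.0125: 1 − 0.0125^(1/330) = 1.32%.
- Wilson upper limit: z²/(n + z²).
  - One-sided, z = 1.960: 3.841/333.841 = 1.15%.
  - Two-sided, z = 2.241: 5.024/335.024 = 1.50%.

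**Step 3: one or two events.** With x observed events, the resampled count follows Binomial(330, x/330). The percentile bootstrap upper limit is the relevant quantile of that count, divided by 330. The exact limit is the corresponding quantile of Beta(x + 1, 330 − x).

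Worked case, x = 1, one-sided 97.5%: under Binomial(330, 1/330), P(count ≤ 2) = 0.920 and P(count ≤ 3) = 0.981. The 97.5th percentile is therefore 3, and the limit is 3/330 = 0.91%. For x = 2, P(count ≤ 4) = 0.948 and P(count ≤ 5) = 0.984, so the limit is 5/330 = 1.52%.

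| Events | Bootstrap, one-sided 97.5% | Exact, one-sided 97.5% | Bootstrap, two-sided 97.5% | Exact, two-sided 97.5% |
|---|---|---|---|---|
| 0 | 0% | 1.11% | 0% | 1.32% |
| 1 | 0.91% | 1.68% | 1.21% | 1.92% |
| 2 | 1.52% | 2.17% | 1.82% | 2.44% |

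The shortfall appears on either reading of sidedness.

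**Step 4: how often this would matter.** P(0 events) = (1 − p)^330.

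| Assumed true rate | P(0 of 330) | Coverage of the one-sided 97.5% bootstrap upper limit |
|---|---|---|
| 0.2% | 51.7% | 48% |
| 0.5% | 19.1% | 81% |
| 1.0% | 3.6% | 84% |

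In the first two rows the only miss is the zero-event result, so coverage is 100% − 51.7% = 48.3% and 100% − 19.1% = 80.9%. At 1.0% the limit also misses when one event is seen, because 0.91% is below 1.0%. These figures describe the bootstrap interval alone, not the required pair of intervals.

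**The case against.** **The rule asks for two intervals.** A reader might infer that the plan would report false certainty of no harm. The documents do not support that. A traditional interval is required alongside, and nothing says it is Wald. If it is exact or Wilson, an upper limit of about 1.1%–1.5% appears beside 0%–0%. This stands. What remains is that the traditional method is unnamed, one common choice fails in the same way, and no rule says which interval to rely on when the two disagree.

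**The sentence may not apply to SAEs.** It follows text on continuous variables and opens with a normality condition. The sentence on proportions names only the effectiveness endpoint, and adverse events have their own instruction to list and summarise. This is a serious argument: applying the bootstrap to the safety endpoint rests on the literal breadth of the wording, and the authors may have intended something narrower.

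**On the narrow reading, a reader might infer that the plan gives the safety endpoint no interval at all.** That goes too far. Part of the SAP was removed before review and may deal with safety analysis, so its absence here cannot be counted as an omission.

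**Nothing passes or fails on this interval.** Correct for the text available: it contains no safety threshold or hypothesis. A reader given 0 of 330 could also work out the exact limit, and related SAEs will be listed as well as counted.

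**The figures for one or two events depend on the bootstrap type.** Also correct. The SAP names none in the available text and defers to a cited reference. The figures assume a percentile bootstrap. The collapse at zero events does not depend on that choice.

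**Conclusion.** The point holds as a reporting defect. Taken literally, the SAP prescribes for the SAE percentage a method that is invalid when events are rare. At 0 of 330 its upper limit is 0%, against an exact 1.11% one-sided or 1.32% two-sided. At one and two events, a one-sided 97.5% percentile bootstrap limit is too low by 1.68 − 0.91 = 0.77 and 2.17 − 1.52 = 0.65 percentage points.

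The conclusion rests on three assumptions: that the broad sentence reaches the SAE percentage, that the safety endpoint is summarised per subject with 330 as denominator, and, for non-zero counts only, that the bootstrap is of the percentile type. The first is the least certain.

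The documents do not show that a misleading safety conclusion would follow. The companion interval may be sound, and no safety decision depends on either. A clarification is still worthwhile, because it settles both the scope of the rule and the choice of method before the data are seen.

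**What to change.** Add to the SAP: the primary safety endpoint is summarised as the proportion of subjects with at least one SAE possibly related to AFM, with an exact (Clopper-Pearson) one-sided 97.5% upper confidence limit; bootstrap and normal-approximation intervals are not used for adverse event proportions. State in advance that 0 of 330 would give an upper limit of 1.11%. If fewer subjects are analysed, the limit rises by the same formula, for example 1 − 0.025^(1/300) = 1.22% for 0 of 300.

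If the removed part of the SAP already names a method for safety proportions, it is enough to limit the broad sentence to the variables it was meant for.

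The cost is a sentence or two of SAP text. No new data or change in conduct is needed, and the bootstrap for the effectiveness endpoint is untouched. The downside is a slightly less favourable safety figure: an upper limit of 1.11% in place of 0% if no event is seen.
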